3 STUDY DESIGN

General description

The “Step-Up” Study will use a randomized experimental design to examine the preliminary efficacy of the physical activity intervention in AYAs who are receiving chemotherapy that will last approximately 12 weeks.

Number of Subjects

Seventy-five AYAs will be recruited from the Froedtert Hospital/Medical College of Wisconsin (FH/MCW) Cancer Center and Children’s Hospital of Wisconsin.

Primary Endpoints

The primary endpoints for the study include self-efficacy for physical activity, self-regulation of physical activity fatigue severity, physical activity, and fatigue severity.

The following table summarizes the proposed instruments for the study:

IFSMT factor	Variable	Measure	Pre	Post
Condition-specific: Individual	Demographics, health history, diagnosis, treatment regimen	Medical Record Review Form	x	
Condition-specific: Individual and family	Individual, household and family characteristics	Individual and Family Information Form	x	
Condition-specific: Individual	Usual amount of PA before diagnosis (self-reported)	Godin Leisure Time Index ⁴¹	x	
Process: Self efficacy	Self-efficacy for PA	Physical Activity Assessment Inventory ⁴²	x	x
Process: Goal-setting and self-monitoring	Self-regulation skills and abilities	Self-Regulation Index for PA ⁴³	x	x
Process: Negotiated collaboration	Perceptions of the intervention, preferred features of the PA tracker and facilitator	Evaluation of Intervention (intervention group only)		x
Proximal outcome: PA behaviors	# days worn, daily and weekly goals, daily step counts	PA and use of PA tracker (Fitbit) (intervention group only)	throughout	
Proximal outcome: PA behaviors	PA (steps/day)	Blinded accelerometer (ActiGraph GTx3+) x 7 days	x	x
Distal outcome: Symptom severity	Intensity of emotional distress, fatigue, pain, physical function, sleep disturbance, satisfaction with participation in social roles	PROMIS-29 ⁴⁴	x	x
Distal outcome: Fatigue severity	Fatigue frequency, duration, intensity and impact of fatigue on activities	PROMIS – Fatigue Short Form ⁴⁴	x	x

Randomization

Patients will be randomized into two groups (intervention and usual care) using the Excel 'RAND' function to create a randomization chart forcing 38 into the intervention arm and 37 into the usual care arm.

Study Timeline

Primary Completion

The study will reach primary completion 19 months from the time the study opens to accrual.

Study Completion

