6. STATISTICAL ANALYSIS

Sample Size

In an a priori power analysis using a mediation model that includes 4 predictors (intervention variable, self-efficacy, self-regulation, and PA), a total sample of 68 participants (34 in each group) would be needed to detect a medium-sized effect at a 0.10 significance level with 80% power. The power analysis was completed by using an online sample size calculator (<http://www.danielsoper.com/statcalc/calculator.aspx?id=1>) based on the above information. Physicians at FH/MCW and CHW saw approximately 300 AYAs with a new cancer diagnosis in 2012, and about half of those AYAs received chemotherapy. Assuming a 50% enrollment rate and 10% attrition, 75 AYAs will be recruited from these sites for a final sample of 68.

Data Management and Analysis

Questionnaire data will be collected electronically using REDcap surveys, and accelerometer (Actigraph) data will be analyzed using respective software. For the intervention group, weekly PA data will be transcribed from the PA tracker (Fitbit Flex) dashboard to REDcap files at each visit. All REDcap data will be exported to SPSS for analysis. Descriptive statistics will be used to describe and summarize the context variables related to the sample. Variables with significant patterns of variation will be explored as potential covariates. Missing values will be identified and reviewed for patterns of missingness, and the percentage of missing data will be calculated. If missing data are less than 5%, pairwise deletion will be used in data analysis, meaning all available cases will be used. If missing data are greater than or equal to 5%, Little's Chi-square test will be used to check if data are missing at random. If missing at random is assumed, multiple imputation method will be used. Field notes from sessions with the facilitator related to barriers and self-management strategies as well as notes from post-study debriefing interviews will be recorded and organized by participant visit.

After all study queries and analyses are completed, the data/PHI will not be destroyed but will be archived in a secure long-term storage site in order to keep an accurate record of screened and enrolled subjects for the sponsor and potential audit purposes only specific for this study. Data/PHI would not be destroyed until permission is granted by the sponsor to destroy the records.

Statistical Analyses

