Specific Aim 1: To determine the impact of the PA intervention on the self-management process variables of self-efficacy and self-regulation, data analysis will examine differences in baseline and post-study measures of self-efficacy and self-regulation for each group. Group differences will be compared using t-tests to determine the effect of the intervention on these process variables. A mediation model will be used to describe the relationships of self-management process variables (self-efficacy and self-regulation) to PA (steps/day by accelerometer) and fatigue severity where self-efficacy and self-regulation are the main mediators of the intervention, PA is the second mediator, and fatigue severity is the dependent variable. The direct and indirect effect of treatment on PA and fatigue severity will be determined by the following steps:^{45, 46}

- Step 1. The regression of the fatigue severity on the intervention variable, ignoring the mediators, is significant.
- Step 2: The regression of the main mediators on the intervention variable is significant.
- Step 3: The regression of the second mediator (PA) on the main mediators (self-efficacy and self-regulation), controlling for the intervention, is significant.
- Step 4: The regression of the fatigue severity on the second mediator (PA), controlling for the main mediators (self-efficacy and self-regulation) and the intervention, is significant.
- Step 5: The regression of the fatigue severity on the intervention, controlling for the mediators, is non-significant and nearly-zero. In this case, the effect of intervention on fatigue severity is indirect through the mediators. If regression of the fatigue severity on the intervention, controlling for the mediators, is still significant, then the effect of treatment on fatigue severity is direct.

From the regression models, unstandardized regression coefficients and their standard errors will be calculated for the associations between the intervention variable and the mediators as well as between the fatigue severity and the mediators. The Sobel test will be used to test if the mediation effect is statistically significant.⁴⁵⁻⁴⁹ Data from field notes from the intervention group participants will be analyzed using qualitative, inductive content analysis procedures to identify themes related to self-efficacy and self-regulation skills.

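### Steps 2 and 3 do not say which of the two main mediators must be significant or tie the two steps to the same one, so the chain cannot show which variable carries the effect

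*Combined protocol and SAP*

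**What the plan says.** Section 6, Specific Aim 1, makes self-efficacy and self-regulation the main mediators, PA (accelerometer steps/day) the second mediator and fatigue severity the dependent variable. Five steps follow. The two at issue are "Step 2: The regression of the main mediators on the intervention variable is significant" and, for Step 3, "The regression of the second mediator (PA) on the main mediators (self-efficacy and self-regulation), controlling for the intervention, is significant". Step 5 then concludes that the effect is indirect if the intervention coefficient, adjusted for all mediators, is non-significant and close to zero. It does not separate the mediators.

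Three other elements of the same section bear on the point:

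- Group t-tests on the two process variables are planned, but are not linked to the steps.
- Coefficients and standard errors are to be calculated for intervention with mediators and for fatigue with mediators. The mediator-to-PA coefficient, which is the subject of Step 3, is not listed.
- A Sobel test is planned for a single mediation effect. The path it covers is not identified.

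**The concern.** A variable mediates only if the intervention changes it and it in turn affects the next variable in the chain. With two candidates, both links must hold for the same one. Steps 2 and 3 do not ask for that. Suppose coaching raises only self-regulation, while only self-efficacy predicts steps/day. Each step can then be significant although neither variable transmits anything.

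The plan could be read more strictly, so that both mediators must be significant in both steps. Step 3 then puts two probably correlated scales into one model, where they share their association with PA, and the rule will often fail when both truly mediate.

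Aim 1 is the primary objective and concerns these two variables. The Theoretical Framework in Section 2 links education with self-efficacy, and the self-regulation resources with self-regulation, so crediting the wrong mediator would credit the wrong component.

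**Working it through.** **The plan's own figure.** Section 6 says "a total sample of 68 participants (34 in each group) would be needed". The target is 80% power at alpha 0.10 for a medium effect, with four predictors. No number is given for medium; I assume f² = 0.15. For the overall R² test, the noncentrality is f² × N = 0.15 × 68 = 10.2 on 4 and 63 degrees of freedom. Power is 79.6% at N = 68, and N = 69 is needed for 80%, so 68 reproduces within rounding. On attrition, 68 / 0.9 = 75.6 and 75 × 0.9 = 67.5, close to the stated 75 and 68. This calculation covers the overall four-predictor test. It says nothing about power for a path through one mediator.

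**Simulation model.** T is the arm (34 per arm):

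- mediator k = a_k·T + error, with correlation r between the two errors;
- PA = b1·M1 + b2·M2 + c·T + error;
- fatigue = g·PA + error.

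Each variable has unit variance within arm. The documents give no path sizes or correlation, so a, b, c, g and r are all assumptions. Four rules were applied at alpha 0.10: joint (Hotelling T² in Step 2, 2-df F in Step 3), either, same mediator (one mediator passes both steps), and both required.

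**Crossed case, Steps 2 and 3.** Here a1 = 0.8, b2 = 0.4, and the other paths through the mediators are zero. Step 2 passes on either mediator in 95% of trials and the Step 3 joint F in 93%.

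- Untied: 0.95 × 0.93 = 0.88.
- Same mediator: about 0.95 × 0.10 + 0.10 × 0.93 = 0.19, slightly too high because of overlap.
- Both required: about (0.95 × 0.10) × (0.93 × 0.10) = 0.01.

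**Both-real case.** Here a = 0.5 and b = 0.25 for each mediator, with r = 0.5. Both mediators pass Step 2 in 51% and Step 3 in 30%: 0.51 × 0.30 = 0.15 (14% on repetition).

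Simulated pass rates for Steps 2 and 3 together:

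| Assumed truth | Joint | Either | Same mediator | Both required |
|---|---|---|---|---|
| Crossed: a 0.8, b 0.4 | 83-88% | 88% | 17-18% | about 1% |
| Crossed: a 0.5, b 0.36, r 0.3 | 52% | 63% | 14% | 1% |
| Crossed: a 0.8, b 0.5, r 0.3 | 92% | 95% | 19% | 1% |
| Both real: a 0.5, b 0.25, r 0.5 | 63% | not tabulated | 65% | 14% |
| Both real: a 0.5, b 0.36, r 0.7 | 61% | 76% | 73% | 37% |
| Both real: a 0.5, b 0.2, r 0.7 | 54% | not tabulated | 43% | 2% |

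**Full chain in the crossed case.**

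- Nothing else acts (c = 0): the intervention has no effect on fatigue, so Step 1 passes in about 10%. All five steps pass in about 3-4%.
- The intervention acts directly on fatigue (assumed -0.5 SD): about 3-8%.
- The intervention also raises PA by another route (c = 0.5 to 0.8 SD): about 19-51%, against 4-10% under the same-mediator rule. Repeating this with g from -0.4 to -0.6 gives 13-51% against 3-9%. A wider grid (c up to 1.0 SD) gives 8-68% against 2-13%.

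One entry in full, for c = 0.8, g = -0.6, a1 = 0.8, b2 = 0.5, r = 0.3: Step 1 passes in 62%, Steps 2 and 3 jointly in 92%, Step 4 in 100%, and Step 5 is non-significant in 89%. The product is 0.62 × 0.92 × 1.00 × 0.89 = 0.51; the simulated joint pass is 52%, against 10% under the same-mediator rule.

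**The case against.** The strongest case is that this is an unclear sentence in an exploratory pilot, and that the rest of the section limits the harm.

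- **No joint test is stated.** A reader might infer that the two mediators are tested as one block. The text does not say so; Step 2 has two dependent variables, so two regressions are a natural reading. This stands: the documented fault is an unspecified rule. The either reading has the same crossed-path problem.
- **Joint testing does not make the chain fail when both mediators work.** A reader might infer that it does. The joint rule is level with the same-mediator rule in one setting (63% against 65%), worse in another (61% against 73%) and better in a third (54% against 43%). Severe failure belongs to the both-required reading.
- **The 83-88% is not a rate of false conclusions.** The plan concludes only at Step 5, and the full false pass is about 3-4% when nothing else acts. This stands. The protection comes mainly from Step 1, however, and weakens when the intervention reaches PA by another route. Section 2 makes such a route plausible: it lists continuing collaboration with the facilitator as a third component and names social facilitation, which the mediation model omits.
- **In that situation mediation through PA is real.** This also stands. A general conclusion of an indirect effect is then not simply false; attribution to self-efficacy or self-regulation is.
- **The t-tests and Sobel test may help.** The t-tests show which mediator moved, but not which predicts PA. A Sobel test for each mediator on its Step 2 and Step 3 coefficients would cut the full false pass in the crossed case to 0.4-0.9%. The plan does not say that this is the path tested, and it omits the Step 3 coefficient from its list.
- **Consequences.** A reader might infer that the result decides which component is kept in a later trial. No section says so.

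**Conclusion.** The point holds as a gap in the decision rule. It is more than missing detail, because each available reading can mislead: joint and either readings accept crossed paths, and a both-required reading rejects most true cases at the assumed sizes. The false pass of the full chain is small (about 3-4%) unless the intervention also raises PA outside the two mediators; it is then about 19-51%, and what is wrong is the attribution to a mediator. All of these rates rest on assumed path sizes and correlations. That the two steps are not tied together, that the mediator-to-PA coefficient is not listed and that the Sobel path is unassigned follow from the text alone.

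**What to change.** In Section 6, Specific Aim 1:

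1. Fit Step 2 separately for self-efficacy and self-regulation, and report each mediator's own Step 3 coefficient with its standard error.
2. Estimate two specific serial indirect effects: intervention to self-efficacy to PA to fatigue, and intervention to self-regulation to PA to fatigue. Stopping at PA would omit Step 4 and the dependent variable. Also report each intervention-to-mediator-to-PA effect, since the section promises indirect effects on PA too. Give each a confidence interval, for example by bootstrap.
3. Claim mediation only for a variable whose own indirect effect is supported. Pairing significant steps within a mediator is not enough, since that rule still passes Steps 2 and 3 in 17-18% of crossed trials.
4. Use the 2-df joint test in Step 3 only to say that the two process variables together predict PA.

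The cost is SAP wording and a few more estimates from data already planned. There will be two mediator-specific conclusions, to be labelled exploratory or to share the 0.10 level (0.05 each if split equally). Precision will be limited: in the both-real case with an assumed PA-to-fatigue slope of -0.4, each serial effect is 0.5 × 0.25 × (-0.4) = -0.05 SD of fatigue, and all five steps pass in only about 5% of trials under the joint or the same-mediator rule.

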4. PATIENT SELECTION

Inclusion Criteria

Patients eligible for the study will be:

- 1) between the ages of 18 and 39 years of age;¹
- 2) have a diagnosis of cancer;
- 3) are within the first two months of a chemotherapy regimen that will last at least another 3 months;
- 4) are ambulatory without assistance;
- 5) have written consent from their physician to participate;
- 6) have the ability to understand English;
- 7) have access to a computer and the Internet.

The goal of this study is to deliver the intervention as early in the treatment period as possible, but we recognize that recruiting and completing baseline measures before chemotherapy begins may be a burden to patients and a barrier to recruitment. The lower age limit for AYAs will be set at 18 years rather than 15 years in order to use one set of instruments which have been validated only for adults over age 18 years. AYAs with any diagnosis of cancer will be included in this exploratory pilot study.

Exclusion Criteria

Patients will be excluded from enrolling in the study if they have symptoms of uncontrolled cardiopulmonary disease, uncontrolled neurological disease, delayed wound healing from surgery, a high risk of bone fracture, or pre-existing peripheral neuropathy. Physicians will be asked to give written approval to indicate that patients do not have any of these contraindications to physical activity.

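### Mediation Steps 3 to 5 adjust for no disease or treatment variable, so severity that lowers steps and self-efficacy and raises fatigue may be read as mediation

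*Combined protocol and SAP*

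**What the plan says.** Section 6, Specific Aim 1, writes out the terms of each regression. Step 3 regresses activity (steps/day) on self-efficacy and self-regulation, holding arm fixed. Step 4 regresses fatigue on activity, "controlling for the main mediators (self-efficacy and self-regulation) and the intervention, is significant". Step 5 regresses fatigue on arm, holding the mediators fixed, and concludes from a near-zero arm coefficient that the effect runs through the mediators. A Sobel test follows. The sample-size paragraph is built on the same terms: a "mediation model that includes 4 predictors (intervention variable, self-efficacy, self-regulation, and PA".

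The population is mixed: "AYAs with any diagnosis of cancer will be included in this exploratory pilot study" (Section 4). Patients enter at any point in the first two months of a regimen, and visits follow chemotherapy cycles of 2 to 4 weeks (Section 5). The instrument table in Section 3 shows that the Medical Record Review Form captures "Demographics, health history, diagnosis, treatment regimen" before the intervention. It also shows that fatigue and steps/day are measured before and after.

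The only covariate provision is one sentence in Section 6 under Data Management and Analysis, repeated in the Protocol Summary. It says that variables with significant patterns of variation will be explored as possible covariates.

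**The concern.** Randomisation makes the arms comparable, which protects Steps 1 and 2. Steps 3 and 4 compare patients who reached different levels of self-efficacy and activity for reasons that include how ill they were and how harsh their regimen was. Step 5 conditions on those same post-randomisation variables.

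The protocol itself makes a common cause plausible. Section 2 says that fatigue is worst during treatment and moves with chemotherapy cycles, that activity falls in young adults during chemotherapy, and that health status is a context factor shaping self-management. A sicker patient can therefore have fewer steps, lower self-efficacy and more fatigue without any of these causing another.

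At stake is the reading of the mechanism. The Protocol Summary makes the process variables and their relationships to activity and fatigue the primary objective, and Aim 2 reuses the model.

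**Working it through.** **1. The plan's own figure.** Section 6 gives 68 in total, 34 per arm, as enough "to detect a medium-sized effect at a 0.10 significance level with 80% power". It gives no number for medium; I assume f² = 0.15. For the overall regression F test with u = 4 predictors, v = 68 − 4 − 1 = 63 and λ = 0.15 × 68 = 10.2, power at alpha 0.10 is 79.6%, and 80% is first reached at N = 69. The stated 68 is reproduced to within one patient, which confirms that the powered model has four terms and no clinical covariate. Attrition: 75 × 0.90 = 67.5, or about 68.

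**2. What each step adjusts for.**

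| Step | Regression | Held fixed | Protected by randomisation |
|---|---|---|---|
| 1 | fatigue on arm | nothing | yes |
| 2 | self-efficacy, self-regulation on arm | nothing | yes |
| 3 | activity on self-efficacy, self-regulation | arm | no |
| 4 | fatigue on activity | self-efficacy, self-regulation, arm | no |
| 5 | fatigue on arm | all mediators | no |

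**3. Bias in the model as written.** Assumptions, none of them in the documents: a severity factor U correlates −r with each mediator and +r with fatigue; arm shifts each mediator by d SD; no mediator affects another mediator or fatigue; 34 complete cases per arm; alpha 0.10, borrowed from the power statement. Within arm, the mediators then correlate r² with one another and −r² with fatigue, which gives:

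- Step 3, each process variable on activity: r²/(1 + r²). For r = 0.5: 0.25/1.25 = 0.20.
- Step 4, activity on fatigue (both slope and partial correlation ρ): −r²/(1 + 2r²). For r = 0.3: −0.09/1.18 = −0.076. For r = 0.4: −0.16/1.32 = −0.121. For r = 0.5: −0.25/1.50 = −0.167.
- Step 5, direct arm effect when its true value is zero: +3d·r²/(1 + 2r²). For d = 0.5 and r = 0.5: 3 × 0.5 × 0.167 = +0.25 SD.

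**4. False significance at Step 4.** The test statistic is shifted by δ = |ρ|√63/√(1 − ρ²), and the critical t on 63 df is 1.669. For r = 0.4, δ = 0.97, so the rate is about P(Z > 0.70) + P(Z < −2.64) = 0.242 + 0.004, or 25%. For r = 0.3, δ = 0.61 gives 16%. For r = 0.5, δ = 1.34 gives 37%. Simulation of the full model agrees.

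| r | Step 4, as written | Step 4, half-reliable covariate | Sobel (arm–activity–fatigue), d = 0.5 to 0.8 |
|---|---|---|---|
| 0.3 | 16% | 11–12% | 4–10% |
| 0.4 | 25% | 15–16% | 7–16% |
| 0.5 | 37% | 22–23% | 13–25% |

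The Sobel test uses z = ab/√(a²·s_b² + b²·s_a²), where a is the arm effect on activity and b is the Step 4 slope. It is conservative here: with no severity effect and d = 0.5 it rejects in about 2% of trials. Severity measured without error would return Step 4 to 10%. At Step 3, self-efficacy is falsely significant in 18% of trials at r = 0.3 and 49% at r = 0.5.

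**5. The Step 1 gate.** Proportion of simulated trials passing Steps 1 to 4 with no true mediation, d = 0.5:

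| r | No arm effect on fatigue | Direct arm effect of −0.5 SD |
|---|---|---|
| 0 | 0.1% | 0.6% |
| 0.3 | 0.5% | 2.5% |
| 0.5 | 2.4% | 16.7% |
| 0.7 | 4.4% | 37.4% |

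**6. Cost of covariates at N = 68.** Overall-test power, f² = 0.15: 4 predictors 79.6%; 7 predictors 69%; 8 predictors 67%; 9 predictors 64%. For a single coefficient with partial f² = 0.15, power is about 93.5% with 4 to 10 predictors.

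**The case against.** The strongest reply is that the plan does have a route to covariates. The Section 6 sentence follows directly on the description of context variables, and diagnosis and regimen are among those. A reader who infers that the plan provides for no adjustment at all would be wrong. What stands is narrower: the sentence does not say which variables enter which step, and it selects on observed variation, not on relation to both mediator and outcome.

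Second, a reader might infer that a false mechanism will be reported. The documents do not support that. They give no strength for severity, and at r = 0.3 the inflation is modest. A simpler calculation with only arm and activity in the model gives about 37% at r = 0.4 and 65–67% at r = 0.5, but that is not Step 4. Holding self-efficacy and self-regulation fixed absorbs part of the confounding if severity affects them too.

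Third, the five-step sequence starts with a randomised test. When the arm does not affect fatigue, that gate keeps a false full-mediation verdict rare. It gives much less protection when the arm has a direct effect, and the text does not make the Sobel test conditional on the gate.

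Fourth, this is called an exploratory pilot, and the model is introduced as descriptive. That argues for modest wording, yet Step 5 draws a causal conclusion.

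**Conclusion.** The point holds in a limited form. As written, Steps 3 to 5 may present differences in disease or treatment severity as mediation, and the covariate sentence does not prevent it. Under the assumptions in the working, Step 4 is falsely significant in about 16% to 37% of trials for r from 0.3 to 0.5, and the spurious slope at r = 0.4 is about −0.12 SD of fatigue per SD of steps. These figures illustrate a range and do not predict this trial.

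Two further inferences should be resisted. The treatment comparisons by t-test in Aims 1 and 2 are randomised and are not affected. Nor would adjustment cure the problem: chart variables are proxies for severity, and a half-reliable proxy still leaves about 22–23% at r = 0.5.

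The plan should be changed, because the remedy is cheap and the model serves the primary objective.

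**What to change.** In Section 6, name one short baseline covariate set and use it identically in Steps 2 to 5: baseline fatigue, baseline steps/day, diagnosis group, and one treatment-regimen variable from the Medical Record Review Form. Add time since first dose if the form records it; the instrument table does not list it. Fix the groupings before the data are examined.

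Baseline steps/day belong in the set only if that week precedes the first education session. The Study Calendar places that session at Visit 1 and Section 5 at Visit 2, so the two must be reconciled.

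State that the Step 3 and Step 4 coefficients and the Sobel result are associations conditional on these covariates, with residual confounding possible. Reword the Step 5 conclusion to say that the pattern is consistent with an indirect effect.

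Cost: mainly wording, since the first four items are drawn from measures already scheduled. Four single-term covariates use 4 of the 63 residual degrees of freedom. The four-predictor power statement should be restated or given a note: overall-test power at N = 68 is about 69% with 7 predictors and 67% with the 8 proposed here (f² = 0.15 assumed), while power for a single coefficient is almost unchanged.

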Specific Aim 2: To determine the preliminary efficacy of the PA intervention on outcome variables of PA (steps/day by accelerometer) and fatigue severity, data analysis will examine differences in baseline and post-study measures of PA (steps/day by accelerometer) and fatigue severity (PROMIS-29 and PROMIS Fatigue scores) for each group. Group differences will then be compared using t-tests to detect the effect of the PA intervention on these outcomes. Direct and indirect effect of the intervention on fatigue severity will be studied using the mediation model discussed in Aim 1. Quantitative data about the fidelity of the intervention will be used to estimate the dose of the delivered intervention for each participant and to explore whether there was a dosage effect on the outcomes.

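### Step 5 of the mediation analysis reads a non-significant, near-zero direct effect as proof that the effect is indirect, with no margin or interval, although 68 participants leave direct effects of about 0.4 SD unexcluded

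*Combined protocol and SAP*

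**What the plan says.** Section 6, Specific Aim 1, sets out a five-step regression sequence. Self-efficacy and self-regulation are the first mediators, physical activity (steps/day) is the second, and fatigue severity is the outcome. Steps 1 to 4 each require a significant regression. Step 5 then looks at the intervention coefficient for fatigue and draws its conclusion if that regression, "controlling for the mediators, is non-significant and nearly-zero. In this case, the effect of intervention on fatigue severity is indirect through the mediators". If the coefficient stays significant, the effect is called direct. A Sobel test of the mediated effect is also planned.

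Step 5 gives no significance level, no numerical meaning for near zero, and no confidence interval or equivalence test.

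Under Sample Size, the calculation is for a "mediation model that includes 4 predictors (intervention variable, self-efficacy, self-regulation, and PA"), and states that "a total sample of 68 participants (34 in each group) would be needed". The stated target of that calculation is "to detect a medium-sized effect at a 0.10 significance level with 80% power". No power is given for the direct-effect coefficient.

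Specific Aim 2 relies on the same sequence: "Direct and indirect effect of the intervention on fatigue severity will be studied using the mediation model discussed in Aim 1".

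**The concern.** Saying that an effect runs through the mediators because the remaining coefficient is small and non-significant is a claim that a path is absent. Such a claim needs evidence that bounds the path, usually an interval lying inside a stated margin. A p-value above a threshold does not supply it, and a point estimate described as nearly zero does not either when nobody has said how near.

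Two features sharpen this. First, the direct effect is estimated with adjustment for three variables that the intervention is meant to move. The more strongly it moves them, the larger the standard error of the direct effect and the easier it is to be non-significant. Second, Aim 1 is the primary objective, and Aim 2 reuses the model.

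Other routes to fatigue are plausible. The intervention group has 30-minute coaching sessions, the usual care group has engagement visits, and fatigue is self-reported on PROMIS instruments. Step 5 gives no safeguard against setting such routes aside on data that cannot exclude them. Adding a label for partial mediation would not help, because non-significance would still be read as absence.

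**Working it through.** **Inputs from the protocol (section 6, Sample Size):** 68 analysed, 34 per group; four predictors, so residual df = 68 − 5 = 63; alpha 0.10; power 80%; a medium-sized effect with no number attached.

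**Assumptions:** two-sided alpha 0.10 for Step 5, which states none; f² = 0.15 for medium in the four-predictor model; 0.5 SD and 0.3 SD as example direct effects. The protocol gives no fatigue SD or mediator correlations.

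**1. The plan's own figure.** Overall F test of R² with 4 and 63 df and noncentrality 0.15 × 68 = 10.2: power is 79.6% at N = 68, and N = 69 is the first to reach 80%. The stated 68 reproduces. This is power for the model as a whole, not for the intervention coefficient.

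**2. Precision of the direct effect.** In residual-SD units, with variance inflation factor (VIF) 1:
- SE = √(1/34 + 1/34) = 0.2425
- 90% half-width = t(0.95, 63) × SE = 1.669 × 0.2425 = 0.405
- multiplied by √VIF: 0.45 at VIF 1.25 and 0.50 at VIF 1.5

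Step 2 requires the intervention to be related to the mediators, so VIF is above 1.

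**3. The significance test alone, true direct effect 0.5 SD.** The standardised effect is 0.5 / 0.2425 = 2.06. Power ≈ Φ(2.06 − 1.645) = 66.2%, so the miss rate is 33.8%, or 34.6% by the noncentral t with 63 df.

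| Variation | Miss rate |
|---|---|
| VIF 1.1 / 1.25 / 1.5 | 38% / 43% / 49% |
| one-sided 0.10, VIF 1 | 22% |
| two-sided 0.05, VIF 1 | 47% |

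If 0.5 is in units of the total fatigue SD, the mediators explain 0-50% of its variance and VIF runs from 1 to 2, the range at two-sided 0.10 is about 11-58%.

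**4. Adding the near-zero condition.** At VIF 1 and a true 0.5 SD, the estimate falls within ±0.2 SD in about 11% of trials and within ±0.1 SD in about 4%. When the direct effect truly is zero, the corresponding figures are 59% and 32%. A tight reading therefore protects against error but usually fails even when the direct path is absent.

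**5. The whole rule.** Simulation with 34 per arm, two-sided alpha 0.10 and within-arm SDs of 1. Assumed: arm effect on each process variable 0.5 or 0.8 SD, their correlation 0.4, R² of activity on them 0.2, and activity explaining 10-20% of fatigue variance. The implied indirect effect is 0.08-0.19 SD. Steps 2 and 3 were read leniently (either mediator for Step 2, a joint test for Step 3).

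| Condition met | Direct effect 0.5 SD | Direct effect 0.3 SD |
|---|---|---|
| Step 5 non-significant, nothing else | 30-39% | 65-69% |
| Steps 1-4 passed, Step 5 non-significant | about 9-22% | about 10-31% |
| The same, and estimate under 0.2 SD | about 1-4% | about 1-8% |

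The 90% half-width in these runs was 0.39-0.44 SD, in line with item 2.

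**The case against.** **The rule has several conditions.** Steps 1 to 4 must all be significant, and Step 5 needs a small estimate as well as a non-significant one. A reader might infer from the one-third miss rate that the trial would wrongly declare a wholly indirect effect in a third of cases. The documents do not support that. The last row of the table is the relevant rate, and it is low. This objection stands in full against the stronger reading. It does not rescue the inference: Steps 1 to 4 do not test whether the direct path is absent, and a larger direct effect acting in the same direction as the indirect one makes Step 1 easier to pass. The low rate also depends on a 0.2-SD cut-off that the plan does not contain.

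**The effect size is assumed.** The protocol says only medium-sized. If f² = 0.15 were applied to the intervention coefficient alone, it would correspond to √10.2 × 0.2425 ≈ 0.77 residual SD, missed only about 6-7% of the time. This stands: the miss rates are illustrations. The half-width of about 0.4 SD needs no assumed effect size.

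**The Sobel test is planned too.** It asks whether an indirect effect exists. It says nothing about whether a direct effect is absent.

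**This is an exploratory pilot following a cited mediation approach.** The model is meant to describe relationships, and usual care participants also meet the facilitator. A reader might infer that the plan claims its theory explains the entire effect, or that coach attention and expectation are ruled out. The text does not say so; it says only that the effect is indirect through the mediators. The pilot setting limits the weight of the point, but does not justify a conclusion of absence.

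**Conclusion.** The point holds as a flaw in the standard of evidence. Step 5 turns a non-significant and undefined near-zero coefficient into a statement that the effect is indirect, and nothing else in section 6 supplies evidence that the direct path is absent. With 34 per group and two-sided alpha 0.10, the 90% interval reaches about 0.4 SD either side of the estimate, so the study cannot be expected to show a wholly indirect effect.

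The practical risk of a wrong declaration is modest if near zero is applied strictly, and appreciable if it is not. Those simulated rates rest on the assumed mediator effects, correlations, direct-effect sizes and alpha listed above. No design, sample-size or model change follows; this is a correction to how one result will be interpreted.

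**What to change.** In Step 5, delete the inference from a non-significant, near-zero coefficient to an indirect effect. Replace it with wording such as: *The direct effect of the intervention on fatigue severity, adjusted for the mediators, will be reported with its 90% confidence interval. Non-significance will not be taken as absence of a direct effect. Unless the whole interval lies within a margin stated before analysis, the direct effect will be reported as unresolved.*

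State the margin and the significance level for Step 5. Add that, with 68 participants and an expected half-width of about 0.4 SD, the study is not expected to establish a wholly indirect effect. Apply the same wording where Aim 2 refers back to the model.

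The cost is a text change. The interval comes from a regression already planned, with no new data or visits. The downside is that the trial gives up a claim of complete mediation, which its size is not expected to support.
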